## **Statistical Analysis Plan**

### 4. STUDY METHODS

## 4.1. General Study Design and Plan

This is a 96 week extension study of open-label simufilam 100 mg b.i.d. for subjects who completed the Phase 2 study, PTI-125-04 or who already completed participation in the PTI-125-09 study through Week 96 visit and reconsented to resume participation in the study through FDA approval of simufilam or program termination (Figure 1). All subjects will provide consent to enroll into this study. Simufilam will be administered as coated oral tablets.

The last study visit, Month 24, from the PTI-125-04 study will be used for the Study Day 1 visit assessments in this extension study. Clinic visits will occur every 12 weeks ±10 days as outlined in Table 1– Schedule of Events for Active Participants.

Subjects who already completed participation through Week 96 in PTI-125-09 will have the option to return to the study and resume participation. After the subject provides consent, the Investigator will confirm that the subject continues to satisfy both the inclusion and exclusion criteria. The study drug will be administered at the research site on Re-entry Day 1 and subsequent visits will be scheduled. The length of their participation gap will dictate which visits apply to them according to Table 2 – Schedule of Events for Reentry Participants.

For active subjects, a full physical examination (general appearance, chest/lungs, heart, abdomen, skin, musculoskeletal, Neurologic, Vascular, and Immunologic) will be performed at Study Day 1, Week 48, and Week 96, and Repeat Visit B until study end. For re-entry subjects, a full physical examination will occur on Re-entry Day 1 and Repeat Visit B thereafter until study ends. All subjects will return to the clinic every 12 weeks for AE monitoring, vital sign measurements, height, weight, Columbia Suicide Severity Rating Scale (C-SSRS) Since Last Visit version, and drug dispensation and accountability. Some re-entry participants will require a Re-entry week 4 visit. A brief physical exam (general appearance, cardiovascular, pulmonary, and abdominal examination, as well as an examination of any other system in response to subject-reported symptoms) will occur at all visits that do not have a full physical exam.

Blood draws for clinical laboratory testing, urine collection for urinalysis, and ECGs will be performed at Study Day 1, Weeks 24, 48, 72, and 96, Re-entry Day 1 (if applicable), Re-Entry Week 4 (if applicable), and Repeat Visit B until study end.

[figure not shown]
Safety will be evaluated by adverse event monitoring, to include all procedural assessments (e.g., vital signs, clinical labs, ECGs, physical exam, and the C-SSRS), if results of these assessments meet the definition of an AE or SAE, as determined by the Investigator.

[figure not shown]

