### 2.2. SAFETY PHARMACOLOGY AND TOXICOLOGY

A robust nonclinical ADME, safety pharmacology, and general and genetic toxicology program has been conducted with simufilam. In vitro metabolic profiling showed minimal metabolism across several species including humans. Simufilam was rapidly absorbed and eliminated in in vivo studies in rat and dog with nearly 100% oral bioavailability, a 2.67-h half-life in dog, dose-proportional PK and no accumulation. Simufilam does not inhibit or induce major CYP450 enzymes, nor is a substrate or inhibitor of major human drug transporters at clinically relevant concentrations. Safety pharmacology studies showed no adverse effects on gross behavioral and physiological parameters in the Irwin test of CNS toxicity in rats, no adverse effects on respiratory rate, tidal volume or minute volume in the rat respiratory test, and no adverse effects on arterial blood pressure, heart rate and ECG parameters in the dog cardiovascular study. The in vitro hERG test for cardiotoxicity also indicated no adverse effect. A full battery of genotoxicity studies was conducted (in vitro bacterial Ames, in vitro chromosomal aberration, and in vivo rat micronucleus test) and were all negative. An in vitro specificity screen showed no significant activation or inhibition of a panel of 68 receptors, channels, and transporters.

Simufilam was tested in single dose and repeat dose oral toxicity studies of up to 6 months in rats and 9 months in dogs. A 6-month repeat dose oral toxicity study in rats (PTI-125-NC-049) used the same doses as a 28-day study (50, 500 and 1000 mg/kg/day), which found 500 mg/kg/day to be the no-observable-adverse-effect-level (NOAEL). In the 6-month study, the toxicological response was characterized by decreased body weights and adverse structural and functional alterations in the liver of 500 and 1000 mg/kg/day animals, including increased hepatic weight, hepatocellular hypertrophy and vacuolation, single/multiple basophilic/ eosinophilic/clear cell focus, hepatocellular degeneration, pigmentation, and oval cell hyperplasia. The presence of bile pigment was consistent with

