cholestasis. These findings correlated with changes to the clinical chemistry profile, including increased ALP and total/direct bilirubin. Over the 1-month recovery period, there was complete recovery of the hepatocellular degeneration and partial recovery of hepatocellular hypertrophy; other microscopic findings in the liver remained. The NOAEL in this 6-month study was 50 mg/kg/day (equivalent to 300 mg/m²), corresponding to a safety margin of 6- and 1.6-fold based on Cmax and AUC over the 100 mg b.i.d. dose in human subjects. A second 6-month repeat dose oral toxicity study in rats determined the 6-month NOAEL in the rat to be < 125 mg/kg/day, based on hepatocellular vacuolation in both sexes and hepatocellular hypertrophy in females at 125 and 250 mg/kg. We are evaluating whether these liver effects are rat specific.

In a 9-month toxicity study in dogs (PTI-125-NC-050), the no-observable-effect-level (NOEL) of simufilam was 25 mg/kg. The high dose of 200 mg/kg/day was decreased to 150 mg/kg/day after 1 month due to bodyweight loss considered unsustainable for 9 months. Clinical signs were slight hypoactivity and incidences of slight muscle fasciculations early in the study, and salivation. There were no pathology findings, but the high dose was considered adverse due to two unexplained deaths. The 75 mg/kg/day NOAEL (equivalent to 1500 mg/m²) provides 38- and 19-fold safety margins based on Cmax and AUC over the 100 mg b.i.d. dose in subjects.

Simufilam showed no mutagenic or clastogenic responses in a standard battery of genotoxicity assays.

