### 4. SUMMARY OF STUDY DESIGN

This is an extension study of open-label simufilam 100 mg b.i.d. for subjects who completed the Phase 2 study, PTI-125-04 or who already completed participation through Week 96 in PTI-125-09. This extension study will continue through FDA approval of simufilam or program termination (Appendix A). All subjects will provide consent to enroll into this study. Simufilam will be administered as coated oral tablets.

The last study visit, Month 24, from the PTI-125-04 study will be used for the Study Day 1 visit assessments in this extension study. Clinic visits will occur every 12 weeks  $\pm 10$  days as outlined in Appendix B – Schedule of Events for Active Participants.

Subjects who already completed participation through Week 96 in PTI-125-09 will have the option to return to the study and resume participation. After the subject provides consent, the Investigator will confirm that the subject continues to satisfy both the inclusion and exclusion criteria. The study drug will be administered at the research site on Re-entry Day 1 and subsequent visits will be scheduled. The length of their participation gap will dictate which visits apply to them according to Appendix C – Schedule of Events for Reentry Participants.

For active subjects, a full physical examination (general appearance, chest/lungs, heart, abdomen, skin, musculoskeletal, Neurologic, Vascular, and Immunologic) will be performed at Study Day 1, Week 48, Week 96, and Repeat Visit B until study end. For reentry subjects, a full physical examination will occur on Re-entry Day 1 and Repeat Visit B thereafter until study ends. All subjects will return to the clinic every 12 weeks for AE monitoring, vital sign measurements, height, weight, Columbia Suicide Severity Rating Scale (C-SSRS), and drug dispensation and accountability. Some re-entry participants will require a Re-entry Week 4 visit. A brief physical exam (general appearance, cardiovascular, pulmonary, and abdominal examination, as well as an examination of any other system in response to subject-reported symptoms) will occur at all visits that do not have a full physical exam.

Blood draws for clinical laboratory testing, urine collection for urinalysis, and ECGs will be performed at Study Day 1, Weeks 24, 48, and 96, Re-entry Day 1 (if applicable), Re-Entry Week 4 (if applicable), and Repeat Visit B until study end.

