### 7.1. STOPPING CRITERIA

Liver chemistry threshold stopping criteria have been designed to ensure subject safety and to evaluate liver event etiology during administration of study drug. Potential discontinuation of study drug for abnormal liver function tests should be considered by the Investigator in consultation with the designated medical monitor if the study subject meets one or more of the following criteria:

- ALT or AST  $\geq 4x$  ULN;
- ALT or AST  $\geq 3x$  ULN and total bilirubin  $\geq 2x$  ULN;
- ALT or AST ≥ 3x ULN if associated with the appearance or worsening of fatigue, nausea, vomiting, right upper quadrant pain or tenderness, fever, rash and/or eosinophilia; or
- ALP elevations, if deemed of liver origin and drug-related as follows:
  - o ALP > 3x ULN;
  - o ALP > 2.5x ULN and total bilirubin > 2x ULN; or
  - o ALP > 2.5x ULN if associated with the appearance or worsening of fatigue, nausea, vomiting, right upper quadrant pain or tenderness, fever, rash and/or eosinophilia.

In the event of discontinuation due to abnormal liver function tests, the subject will be appropriately investigated to determine the potential cause and referred to a physician experienced in the treatment of hepatic disorders.

Study drug should be discontinued if a subject: (1) positively affirms suicidal ideation in response to questions number 4 or 5 in the suicidal ideation section of the C-SSRS, or (2) reports any suicidal behavior or non-suicidal self-injurious behavior since their last visit in response to the C-SSRS Suicidal Behavior questions. The subject should be referred to a psychiatrist or an appropriate health care professional for further evaluation and management.

An additional stopping criterion will be bodyweight loss of  $\geq$  2 kg resulting in a BMI < 18.5.

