### 7.2. EVALUATIONS BY VISIT

### 7.2.1. Study Day 1 (Dosing initiation)

Subjects who complete PTI-125-04 will be eligible to consent to this open-label extension. The Study Day 1 visit will occur in conjunction with the Month 24 visit of PTI-125-04.

Subjects will come to the clinic and, in addition to the Month 24 Visit activities for PTI-125-04, the following will be conducted:

Informed Consent

The following end of study procedures required at the Month 24 Visit for the completion of study PTI-125-04 will serve as baseline information for this open-label extension study:

- Review of concomitant medications
- Full physical examination including measurement of vital signs (blood pressure, temperature, pulse, and respiratory rate), height, weight
- C-SSRS Since Last Visit version. If the C-SSRS indicates imminent risk for suicidality, defined as the subject positively endorsing questions 4 or 5 of the suicidal ideation section or any suicidal behavior questions, discontinue study drug and refer for appropriate care.
- Blood and urine sample collection for clinical laboratory tests
- ECG
- Adverse event monitoring

Subjects will be administered one (1) tablet of study drug at the clinic. Subjects will be discharged with their supply of study drug until the next visit. They will be instructed

to take study drug twice daily, with or without food. A dose can be up to 4 hours late, but if a dose is missed, the next dose should NOT be doubled.

For all follow-up visits, subjects will be instructed to bring their study drug bottle to the clinic and a new bottle of study drug will be dispensed.

All follow-up visits can be  $\pm 10$  (ten) days for flexibility.

### 7.2.2. Follow-up Visits on Weeks 12, 36, 60, and 84

Subjects will return to clinic and the following assessments will be conducted:

- Height
- Weight
- Brief physical exam
- Measure vital signs (blood pressure, temperature, pulse, and respiratory rate)
- Adverse event monitoring
- Use of concomitant medications
- C-SSRS Since Last Visit version. If the C-SSRS indicates imminent risk for suicidality, defined as the subject positively endorsing questions 4 or 5 of the suicidal ideation section or any suicidal behavior questions, discontinue study drug and refer for appropriate care.
- Receive and count remaining tablets in each returned bottle of investigational product to assess adherence to BID dosing.

### 7.2.3. Follow-up Visits on Weeks 24 and 72

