### 10.2. SAFETY ANALYSIS

Adverse events reported on case report forms will be mapped to preferred terms and organ systems using the MedDRA mapping system. Vital signs and clinical laboratory results will be descriptively summarized in terms of change from screening values.

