**eClinical Suite** 

## Table 1 - Schedule of Events for Active Participants.

STUDY PROCEDURE	Study Day 1	Week 12	Week 24	Week 36	Week 48	Week 60	Week 72	Week 84	Week 96	Repeat Visit A e	Repeat Visit B f	End of Study / Early Term
Informed Consent	X											
Vital Signs	X b	X	X	X	X	X	X	X	X	X	X	X
Height & Weight	X b	X	X	X	X	X	X	X	X	X	X	X
Physical Examination	Xbe	*	*	*	Χ°	*	*	*	Χ°	*	Хс	X °
Chemistry, Hematology, Urinalysis	X b		X		X		X		X		X	X
ECG	X b		X		X		X		X		X	X
Drug Dispensation d	X	X	X	X	X	X	X	X	X	X	X	
Drug Accountability		X	X	X	X	X	X	X	X	X	X	X
Adverse Events	X b	X	X	X	X	X	X	X	X	X	X	X
Concomitant Medications	X b	X	X	X	X	X	X	X	X	X	X	X
C-SSRS – Since Last Visit	X b	X	X	X	X	X	X	X	X	X	X	X

\* Brief physical exam.

<sup>e Repeat Visit A occurs 12 weeks following the Week 96 visit and then reoccurs every 24 weeks thereafter. f Repeat Visit B occurs 12 weeks following the first Repeat Visit A and then reoccurs every 24 weeks thereafter.

<sup>a Study Day 1 will take place during the Month 24 Visit for study PTI-125-04.

<sup>b Data collected at Month 24 Visit for study PTI-125-04 will be used.

<sup>c Full physical examination at Day 1 (as part of Month 24 Visit from study PTI-125-04), Week 48, Week 96, and Repeat Visit B, and at End of Study or Early Term Visit.

<sup>d Drug will be dispensed at Study Day 1 and every 12 weeks.

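### Body weight is measured at every visit and has its own stopping criterion, but no summary of on-treatment weight change is planned, and the SAP is inconsistent on whether weight will be listed

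*SAP*

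**What the plan says.** **Collection.** Protocol section 4 states: "All subjects will return to the clinic every 12 weeks for AE monitoring, vital sign measurements, height, weight". In the schedules (Protocol Appendices B and C, SAP Tables 1 and 2), "Height & Weight" has a row of its own, separate from vital signs and marked at every visit.

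**Nonclinical findings.** Protocol 2.2 reports that in the 6-month rat study "the toxicological response was characterized by decreased body weights" and by liver changes at 500 and 1000 mg/kg/day. In the 9-month dog study the high dose of 200 mg/kg/day was lowered to 150 mg/kg/day after one month "due to bodyweight loss considered unsustainable for 9 months".

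**Stopping criterion.** Protocol 7.1: "An additional stopping criterion will be bodyweight loss of" at least 2 kg that takes BMI below 18.5. Both conditions must hold.

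**Analysis.** Protocol 10.2 plans AE coding and one further item: "Vital signs and clinical laboratory results will be descriptively summarized in terms of change from screening values". SAP 3.1 withdraws the vital-sign, laboratory and ECG summaries. SAP 4.1 then reads "Safety will be evaluated by adverse event monitoring, to include all procedural assessments (e.g., vital signs, clinical labs, ECGs, physical exam, and the C-SSRS"), with the condition that the investigator considers the result an AE or SAE. SAP 6.3.1 rules out analyses by timepoint.

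**Listings.** SAP 6.3.2 says everything on the eCRF goes into the safety listings, and SAP 6.4.1 says all data will be listed by subject. The SAP section 9 index contains only disposition, demographics/baseline and AE outputs.

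**The concern.** Long-term safety is the study's only objective. Weight is a variable the protocol itself treats as relevant to safety: it appears in the toxicology summary, is measured every 12 weeks and can end treatment. Even so, no planned table would show whether weight fell on treatment, by how much, or in how many subjects.

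The remaining route depends on individual investigators. Protocol 9.1 gives no weight threshold for an AE and relies on observed events, spontaneous reports and a non-specific question to the subject. A slow loss spread over several visits might or might not be entered. If it is entered unevenly, the AE tables will not describe average change or the share of subjects with a sizeable loss, although the data to do so have been collected.

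**Working it through.** The plan gives no figure on weight, so there is none to reproduce. The check is a search for any output covering weight, followed by two illustrative calculations.

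**1. Is weight change summarised anywhere?**

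| Place | Content | Covers weight change? |
|---|---|---|
| Protocol 10.2 | AEs; change in vital signs and laboratory results | Not named. Protocol 7.2 lists vital signs as blood pressure, temperature, pulse and respiratory rate, with weight apart |
| SAP 7.1 | Disposition and reasons for stopping treatment | Only as a reason for stopping |
| SAP 7.3 | Baseline characteristics, variables not named | Starting weight at most |
| SAP 8.1 | Treatment-emergent AEs | Only if entered as an AE |
| SAP 8.2 to 8.5 | Laboratory, vital signs, physical examination, ECG: no listings; significant results go to AEs | No |
| SAP 9 | Seven AE tables, one disposition table, one demographics/baseline table, and matching listings | No |

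**2. Is weight listed?** SAP 6.3.2 and 6.4.1, read literally, say yes. The section 9 index says no. If weight is a separate assessment, nothing in section 8 withdraws the promised listing, but the index lacks it. If weight is part of the physical examination, SAP 8.4 withdraws the listing. Neither reading yields a summary of change.

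**3. Does the 7.1 criterion stand in for a summary?** Inputs: the BMI limit of 18.5 (Protocol 7.1); starting BMI and a height of 1.65 m are assumptions, since the documents give neither.

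- Share of weight to lose = 1 − 18.5/BMI. For BMI 24: 1 − 18.5/24 = 22.9%.
- Kilograms to lose = (BMI − 18.5) × height². For BMI 24: 5.5 × 2.7225 = 15.0 kg.

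| Starting BMI | Loss to reach 18.5 | kg at 1.65 m |
|---|---|---|
| 20 | 7.5% | 4.1 |
| 22 | 15.9% | 9.5 |
| 24 | 22.9% | 15.0 |
| 26 | 28.8% | 20.4 |
| 28 | 33.9% | 25.9 |

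Conversely, a 10% loss takes BMI below 18.5 only from a start below 18.5/0.90 = 20.6, and a 7% loss only from below 18.5/0.93 = 19.9. Subjects who do meet the criterion are not counted in any planned table either, except through a stopping reason or an AE.

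**4. How informative would a summary be?** Half-width of the 95% CI for mean change = 1.96 × SD/√N. The SD is assumed; N = 180 is the ceiling in Protocol 5.1 and 10.3.

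| Assumed SD (kg) | N = 180 | N = 90 (assumed, half the ceiling) |
|---|---|---|
| 4 | 0.58 | 0.83 |
| 5 | 0.73 | 1.03 |
| 7 | 1.02 | 1.45 |

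For the share of subjects crossing a chosen loss threshold, exact 95% intervals at N = 180 would be 2.3% to 9.3% for 9 subjects (5%), 6.0% to 15.3% for 18 (10%), and 14.4% to 26.6% for 36 (20%). These shares are assumed. The intervals only gauge precision; the SAP plans no inferential statistics and the fix needs none.

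**The case against.** The case for leaving the SAP alone is substantial. It is an abbreviated plan for a terminated programme, with no full study report expected and the data intended for the DSUR. It openly replaces objective summaries with AE reporting. The list in SAP 4.1 is illustrative, so weight is not shut out of that route. Protocol 7.2.1 describes the full examination as including "measurement of vital signs (blood pressure, temperature, pulse, and respiratory rate), height, weight", which allows weight to be read as an examination item handled by SAP 8.4 like the other dropped results. Protocol 9.1 requires AEs to be recorded whatever their cause, so putting a loss down to the disease would not excuse omitting it. A DSMB monitors safety throughout. All of this stands, and it lowers the urgency. It does not supply a summary of weight change.

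Four stronger readings are tempting and are not supported:

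- *Weight loss will go unreported unless it becomes an AE.* The two general listing statements, read literally, include weight, and disposition reports reasons for stopping.
- *The plan would miss drug-related weight loss.* The study is open-label with no control arm; no weight summary here could show that a loss is due to the drug.
- *The 7.1 criterion exists because of the animal findings.* Protocol 7.1 gives no rationale. The dog finding arose above the 75 mg/kg/day NOAEL, which has 38- and 19-fold margins. The rat findings were at 500 and 1000 mg/kg/day against a 50 mg/kg/day NOAEL, whose margins (6- and 1.6-fold) also reflect the liver findings.
- *The stopping rule is too lax.* The BMI arithmetic shows only that the rule is not a substitute for a summary; it says nothing about what the rule should be.

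**Conclusion.** The point holds as a modest, inexpensive improvement. No summary of on-treatment weight change is planned in Protocol 10.2 or the SAP, and the SAP's general listing statements do not agree with its own index. As written, weight change enters the summary tables only through an investigator's AE entry or a discontinuation reason.

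How much this matters depends on quantities the documents do not give. Under the assumed starting BMIs of 20 to 28, losses of 7.5% to 33.9% are needed to reach the BMI limit, so many sizeable losses would not surface through the criterion. The half-width of about 0.6 to 1.0 kg rests on an assumed SD of 4 to 7 kg and on 180 subjects with complete data. It is a best case, because 180 is an enrolment ceiling. Change from the extension's baseline also leaves out any change during PTI-125-04, in which 18 of the 24 months were open-label simufilam (12 + 6, Protocol 2.3).

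**What to change.** Amend the SAP before database lock:

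1. **Table (sections 8 and 9).** Add one descriptive table of change and percent change in weight from the extension baseline to the last on-treatment value. Baseline is the PTI-125-04 Month 24 value, and Re-entry Day 1 for the re-entry period. State this explicitly, since Protocol 10.2 refers to screening values and the schedules have no screening visit. Add results by visit only if SAP 6.3.1 is amended to allow them.
2. **Counts in the same table.** Show subjects by largest percent loss, in categories fixed beforehand, and the number meeting the Protocol 7.1 weight criterion exactly as written.
3. **Listing.** Add a by-subject weight and BMI listing to the section 9 index, and reconcile SAP 6.3.2 and 6.4.1 with that index and with SAP 8.2 to 8.5.
4. **Interpretation.** State that the results are descriptive and cannot be attributed to the drug without a control arm, and that any precision quoted for 180 subjects is a best case.

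The cost is SAP wording, one table and one listing from data already collected: a little extra programming in an abbreviated close-out. No change to the stopping rule is proposed.
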